Double blind, randomized, sham-controlled trial parallel arm study that will assess the effectiveness and patient perception of the benefit of the Sana Pain Reliever in individuals with chronic pain.

Device:

The Sana Pain Reliever (Sana PR) by Sana Health Inc is a device comprised of one (1) main component (Mask with Earbuds) and two (2) ancillary components (Charger and Headband). The device is worn over the eyes (with earbuds in ears). The device pulses light at a single wavelength but various frequencies throughout a specific firmware algorithm. Through the earbuds, the device also plays different tones in conjunction with the pulses. The device has a skin contacting Heart Rate Variability (HRV) sensor built into the forehead area that measures HRV throughout use.

- Real Arm

Each session with the device will last 15 min and run under the device's normal settings. The session consists of periods of light/sound pulsing at three distinct pulse frequencies; ~8Hz, 3Hz, and 1Hz. For each frequency, there are distinct sections where the audio and visual pulses vary from eye to eye, and ear to ear.

- Sham Arm

Each session with the device will last 15 min and run under the device's sham setting. For the Sham arm, the device will have the light on for 5 min, off for 5 min and then on again for 5 min. Ear plugs will be used in place of headphones. There will be no sound from the device in the sham group.

Application:

The application being used in this study was designed by Sana health specifically for this study. The application controls the Sana Pain Reliever device and allows users to use the device. Users must use the application to start each session with the device, but the device permits multiple, sequential uses of the device without requiring an interaction with the application. The application will be given to participants of this study on a tablet device. Participants will also be given the charging equipment for the device. The application is HIPAA compliant and will undergo InfoSec review at Mount Sinai. Participants will use the application on a tablet device that will be loaned to them for the duration of the study. The application will track data for this study during the at-home portions of the study between the two baseline visits, over the course of the intervention and between the follow-up visits.

- At-home intervention period (week 2 - 10) - tablet and Sana device:

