Informed Consent: Participants who fulfill the inclusion/exclusion criteria will be consented to the study at the Abilities Research Center at the start of their first in-person study visit or remotely via a telephone call to talk through the consent form followed by completion of the E-Consent process ahead of their first teleconferenced study visit.

Study devices (mask and tablet) will be shipped together ahead of the first visit for those not completing in-person visits. They will be activated and deactivated remotely at the appropriate times. Those completing study visits in person will receive and return their devices at different stages of the trial (described below).

INITIAL BASELINE CLINICAL ASSESSMENT (Week 0) - AT THE ARC OR VIA VIDEO CALL

Screening: After consent has been obtained participants will complete the Beck Depression Inventory (BDI) at the initial baseline visit. Individuals who score greater than 30 pts on the scale (Severe or Extreme Depression) will be withdrawn from the study.

Participant Information will be collected including:

- Age, gender, name and contact information (phone number(s) and email address).
- Current medications: the list of medications will be collected to add to each participant's Sana Health application.
- A self-reported medical history
- Documentation of the location of their pain on a body chart
- Documentation of what pain management techniques participants typically use

Participants will then complete the following questionnaires:

- Neuropathic Pain Symptom Inventory (NPSI)
- Pittsburgh Sleep Quality Index (PSQI)
- Beck Depression Inventory (BDI)
- Patient health Questionnaire Type 9 for Depression (PHQ-9)
- General Anxiety Disorder 7-item questionnaire (GAD-7)
- World Health Organization Quality of Life BREF (WHOQOL-BREF) & World Health Organization Quality of Life Pain (WHOQOL-pain)

Study Devices: Participants will be loaned a tablet device with the Sana application installed. Participants will be instructed on how to use the device and application.

BASELINE PAIN MONITORING (Week 0 - 2) - AT THE HOMES OF THE PARTICIPANTS

Participants will be asked to use the study tablet with the Sana application daily, at night prior to going to sleep. Participants will be asked to complete a Visual Analog Scale (VAS) of how they slept the night prior, a VAS of their amount of pain and asked to report the medications and strategies they used that day for pain management.

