- Participants will be loaned a Sana PR device, earplugs, a charging cable and a strap to secure the device on their head
- The research team will download the Sana Health application on a tablet device compatible with the application that will be loaned to participants (this device will be a tablet that has all functions not necessary to the functionality of the Sana application disabled). The device will be loaned to participants for the duration of the 8-week intervention.
- The research team will teach the participant how to use the Sana PR device and the Sana Health application. Participants will be given an instruction manual for the device and mobile application.

Participants will be instructed to call the lab's direct phone-line [contact] if they have any additional questions when using the device at home.

- Participants will then complete their first 15 min session under the supervision of the research team. For the Sham arm, the device will have the light on for 5 min, off for 5 min and then on again for 5 min. Ear plugs will be used in place of headphones. There will be no sound from the device in the sham group. This familiarity session will ensure the subjects know how to properly use the devices and that there are not

any adverse events (AEs) from the first use of the device. Participants will be instructed to call the lab's direct phone-line [contact] if they experience an AE when using the device at home.

Safety monitoring: A member of the research team will call the participant 48 hours after the first session with device to check for AEs, difficulties using the device and answer any questions.

INTERVENTION (Week 2 - 10) - AT THE HOMES OF THE PARTICIPANTS

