Devices: Participants will be instructed to use the Sana PR every time they experience pain during the day (ad libitum). There will be no minimum or maximum number of uses. Participants will open the Sana Health application and will be prompted to answer the amount of pain they are feeling in the moment using the VAS on the Sana Health application. If it is the first time the participant is using the device for the day, they will also be prompted by the application to complete a VAS to report on how they slept the evening prior. Participants will then turn on the devices using the application. Participants will complete a 15-min cycle with the device. Participants may complete multiple, sequential uses of the device without requiring them to interface with the application. Participants will be prompted to answer the amount of pain they are feeling in the moment after using the VAS on the Sana Health application.

Participants will also be asked to use the Sana PR device every evening immediately prior to/accompanying falling asleep for the night. Participants will open the Sana Health application and will be prompted to answer the amount of pain they are feeling in the moment using the VAS on the Sana Health application. Participants will then be prompted as to what medication they took for their pain that day. The application will be populated with the medications participants reported at the first baseline visit.

Participants will select from this list of medications. Participants will complete a 15 min cycle with the device.

Every two weeks during the 8-week intervention period participants will receive a message on their cellular devices via text message to complete the NPSI, PSQI, PHQ-9 and GAD-7. Participants will be sent compliance reminders to complete these questionnaires on their phones and on the tablet.

Safety monitoring: Participants will be instructed to contact the research team to report any AE over this period. Compliance will be monitored over the 8 week intervention period. A significant decrease in the compliance during (responding to less than 70% of the last 10 scheduled check-ins) of using the device the 8 week intervention will be considered an indication that a participant may need assistance. A research team member will call the participant to ensure that the reason of the drop in usage of the device is not due to an AE.

POST INTERVENTION FOLLOW UP (Week 10) - AT THE ARC OR VIA VIDEO CALL Participant

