- Responses to questions on ease of device use and the likelihood they would hypothetically continue using the devices in their daily life.

Devices: Participants will be asked to return the tablet with the Sana application at this visit
Safety monitoring: Participants will be asked to report any AEs.

Description of the Source Records that Will Be Used to Collect Data About Subjects

Self-reported

Description of Data that Will Be Collected Including Long-Term Follow-Up

- Age, gender, name and contact information (phone number(s) and email address).
- Current medications: the list of medications will be collected to add to each participant's Sana Health application.
- A self-reported medical history
- Documentation of the location of their pain on a body chart
- Documentation of what pain management techniques participants typically use
- Neuropathic Pain Symptom Inventory (NPSI)
- Pittsburgh Sleep Quality Index (PSQI)
- Beck Depression Inventory (BDI)
- Patient health Questionnaire Type 9 for Depression (PHQ-9)
- General Anxiety Disorder 7-item questionnaire (GAD-7)

- World Health Organization Quality of Life BREF (WHOQOL-BREF) & World Health Organization Quality of Life Pain (WHOQOL-pain)
- Record of changes in medications
- Record of changes in pain management techniques participants typically used - Documentation of the location of their pain on a body chart
- Patient's Global Impression of Change (PGIC)
- Human Factors Questionnaire
- Responses to questions on ease of device use and the likelihood they would hypothetically continue using the devices in their daily life.

4. Subjects

Enrollment goal: 180 participants

Inclusion Criteria

- Confirmed clinical diagnosis of neuropathic pain
- Ages 18+
- Fluent in English
- Consistent medications for the last 4 weeks prior to the first baseline visit (week 0)

Exclusion Criteria

- Diagnosis of photosensitive epilepsy
- Ear or eye infection
- Vision impairments that affect perception of light in one or both eyes
- Deafness in one or both ears
- Psychiatric disorders (participants will not be excluded if they score 0-30 points on the BDI, or if participants self-report having anxiety)

5. Data Analysis plan

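### The only seizure-related exclusion requires an existing diagnosis of photosensitive epilepsy, so a person with another epilepsy or a past seizure, never assessed for light sensitivity, could enter the pulsed-light Real arm

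*Combined protocol and SAP*

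**What the plan says.** The Exclusion Criteria in 4. Subjects have five items. The first is "Diagnosis of photosensitive epilepsy". One other item mentions light, "Vision impairments that affect perception of light in one or both eyes", but it concerns reduced perception. The remaining three deal with ear or eye infection, deafness, and psychiatric disorders.

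In 4. Study Procedures, the week 0 visit has a Screening paragraph that names one instrument: "After consent has been obtained participants will complete the Beck Depression Inventory (BDI) at the initial baseline visit". The same visit collects "A self-reported medical history", with no eligibility decision attached to it.

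The exposure differs by arm. For the Real arm, "The session consists of periods of light/sound pulsing at three distinct pulse frequencies; ~8Hz, 3Hz, and 1Hz". For the sham arm, "the device will have the light on for 5 min, off for 5 min and then on again for 5 min". Randomisation and the first device session take place at week 2, at the centre or by video call. The treatment period is headed "INTERVENTION (Week 2 - 10) - AT THE HOMES OF THE PARTICIPANTS", and on frequency of use it says "There will be no minimum or maximum number of uses". Participants are also asked to use the mask each evening as they go to sleep.

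**The concern.** The protocol excludes people with photosensitive epilepsy from a study of a light-emitting mask, so it recognises a seizure hazard from light for at least that group. The criterion depends on a label, and a label exists only where someone has been assessed and diagnosed. A person with a different epilepsy diagnosis, or with a past seizure that was never followed by an assessment of light sensitivity, has no such label and meets every criterion as written.

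What is at stake is participant safety. If such a person did react to the pulsed light, this could happen at home, possibly at bedtime, with no study staff present. The information that would prompt a closer look may already be in the study file from week 0, but the protocol gives no instruction to act on it.

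**Working it through.** No formula applies and the plan states no figure to reproduce. The check is whether any step between recruitment and home use would catch the person described. The steps, in order:

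1. **Inclusion criteria (4. Subjects).** Neuropathic pain diagnosis, age 18 or over, fluent English, stable medication for 4 weeks. None concerns seizures.
2. **Exclusion criteria (4. Subjects).** Of five items, one concerns seizures, and it requires an existing diagnosis of photosensitive epilepsy. Other epilepsies, a past seizure, and known but undiagnosed sensitivity to flashing light are not covered.
3. **Consent (4. Study Procedures).** People are consented once they are judged to meet the criteria. No further seizure question is described.
4. **Week 0 visit.** The screening rule is a BDI score above 30, which leads to withdrawal. The self-reported history is collected, but no rule acts on it. No light-sensitivity test is listed.
5. **Week 2 visit.** Participants are randomised and complete a first 15-minute session that the research team supervises and checks for adverse events. The visit may be by video call.
6. **48 hours later.** The team telephones to ask about adverse events and difficulties with the device.
7. **Weeks 2 to 10.** Use is at home, as often as wished and in consecutive sessions if wanted, plus every evening. Monitoring consists of adverse events reported by the participant and a call if fewer than 70% of the last 10 check-ins are answered. For the bedtime session the application asks for a pain rating beforehand only, so it collects no rating straight after that use.

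Steps 1 to 4 come before exposure, and none identifies a person with another epilepsy or a past seizure. Steps 5 to 7 are real safeguards, but they act during or after exposure and do not screen for seizure risk.

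**Which arm.** The Real arm receives light pulsed at three frequencies. The sham description has light on and off in 5-minute blocks, with no pulsing mentioned. The exposure at issue therefore belongs to the Real arm.

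**Timing.** History is taken at week 0 and first exposure is at week 2, which leaves two weeks to act. For remote participants the mask is shipped before the first visit but activated remotely, so a week 0 decision can still precede first use.

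**Size.** The number affected would need the share of entrants with such a history, the fraction of them who are light-sensitive, and the chance of a seizure at these frequencies. The documents give none of these. They give only an enrolment goal of 180 and no allocation ratio.

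**The case against.** The strongest reply is that excluding diagnosed photosensitive epilepsy shows a recognised hazard for that group and no other. The documents contain no seizure data for the device and no statement that people with other epilepsies are at risk from it. They do not say whether the narrow wording was deliberate. This stands: it is a gap in coverage and not a contradiction within the protocol. It leaves the gap unexplained, however, and does not close it.

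A second reply is that home use does not begin without any oversight. There is a supervised first session, a 48-hour call, a telephone line for adverse events, a call when compliance falls, and a reminder to seek immediate medical attention after an injury. All of this is correct and belongs in any fair account. None of it bears on who is admitted.

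Third, seizure warnings may exist in the consent pages, which were removed from the text, or in the device manual, which is not supplied. That is possible, but a warning would not change the eligibility criterion.

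Some stronger readings go further than the documents allow:

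- A reader might infer that everyone randomised faces the hazard. The sham light is not described as pulsed, so this is not supported.
- A reader might attach a head-count. Assuming, say, that 1% to 3% of entrants have any seizure or epilepsy history gives 180 × 0.01 = 1.8 to 180 × 0.03 = 5.4 people. That range has no source in the documents, and it counts people with a history, not people who are light-sensitive or expected to have a seizure.
- A reader might infer that one seizure would halt the trial. 6. Safety Assessment sends any adverse event to the IRB to consider whether the study should continue. It sets no rule specific to seizures.

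**Conclusion.** The point holds as a limited gap in eligibility. As written, a person with another epilepsy or a past seizure, whose response to flashing light was never assessed, can be randomised to the Real arm and go on to home and bedtime use with no cap on sessions. This rests on the wording of the criteria and on the absence of any seizure question, light-sensitivity test or rule tied to the week 0 history in the text supplied. It does not rest on any assumed prevalence.

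The size cannot be derived. The documents do not show that such people would be harmed, nor how many would enrol. The change is justified because the possible event is serious and the relevant history can be asked about at a visit that already takes place. It is a worthwhile improvement to the protocol and has no bearing on the validity of the planned analysis.

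**What to change.** Widen the seizure-related exclusion in 4. Subjects beyond an existing photosensitive-epilepsy diagnosis, so that it covers reported epilepsy or seizure history and known sensitivity to flashing light. The sponsor's clinical investigators should set the exact scope, such as how to treat a single remote seizure, against the Real-arm exposure and the home-use instructions in 4. Study Procedures. If they prefer to keep the narrow wording, they should state the reason.

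Apply the criterion from the medical history at week 0, with an explicit question, before randomisation and first device use at week 2 and before remote activation of the mask. The protocol already withdraws people after consent on a week 0 BDI result, so a suitable mechanism exists.

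The cost is one line of eligibility text and one question. Some otherwise eligible people would be excluded, probably few although the documents do not allow a count, and the result would not extend to them. The change has a limit: self-report will not detect photosensitivity in someone with no relevant history, so it narrows the gap without removing it.

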When the brain is given a stimulus, through the eyes or ears, it emits a responsive electrical charge, called a Cortical Evoked Response. These electrical responses, measured via electrodes, travel throughout the brain and is ultimately perceived as vision and audible sound. When the input stimulus resembles a pattern the brain itself uses, the brain responds by synchronizing to it, a process called Frequency Following Response (FFR). The Sana Mask utilizes this above described AVS mechanism to induce FFR. The firmware consists of periods of light/sound pulsing at three distinct pulse frequencies; ~8Hz, 3Hz, and 1Hz. For each frequency, there are distinct sections where the audio and visual pulses vary from eye to eye, and ear to ear.

The website for the device can be found here: <https://www.sana.io/>

Previous Trials Using the Sana PR:

The Sana Pain Reliever device has been in a previous study entitled "Photic Sleep Enhancement During a Mars Analog Exploratory Mission Simulation" that received a Western Institutional Review Board Certificate of Approval (attached). Two abstracts from studies involving the device are also attached.

2. Objectives

Primary: Determine the effectiveness of the Sana PR at reducing chronic pain over an 8-week intervention period and the long-lasting effect of pain relief at a 4-week follow-up using the following outcome measures:

Secondary Objectives:

- 1) Determine the impact using the device for an 8-week intervention has on Quality of Life and Sleep
- 2) At both baseline visits and both follow-up visits participants will complete a body chart on pen and paper to draw out where they feel their pain. Changes to the location of their pain will be measured.
- 3) Determine the tolerability and user acceptability of the devices

3. Device

The Sana Pain Reliever (Sana PR) by Sana Health Inc is a device comprised of one (1) main component (Mask with Earbuds) and two (2) ancillary components (Charger and Headband). The device is worn over the eyes (with earbuds in ears). The device pulses light at a single wavelength but various frequencies throughout a specific firmware algorithm. Through the earbuds, the device also plays different tones in conjunction with the pulses. The device has a skin contacting Heart Rate Variability (HRV) sensor built into the forehead area that measures HRV throughout use.

Figure 1: the Sana mask

4. Study Procedures

Description of the Study Design

Design:

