The application tracks the number of times the device is used in a day and time stamps those sessions. For each session, the application records the HRV data from the forehead sensor of the device and what frequency the auditory and visual stimuli the device emitted during the 15 minutes. Prior to and immediately after each session the application will ask users to rate the amount of pain they are feeling in the moment on a Visual Analog Scale (VAS) along a number line from "no pain" to "worst imaginable pain". The first time the device is used each day, participants will be asked to complete a VAS for how they slept from the night prior. For the last use of the device prior to going to sleep for the day, participants will only be asked to complete the VAS prior to using the device to not disrupt sleep patterns. Additionally, at the last use before sleep participants will be asked to select which of their medication for pain management they took that day. The medications will appear in a drop-down menu on the application. Medications will be reported by each individual to the research team at the first baseline visit week 0 and will be inputted by the research team into each participant's application. Every two weeks during the 8-week intervention period the application will also prompt users to complete the following additional questionnaires: the Neuropathic Pain Symptom Inventory, the Pittsburgh Sleep Quality Index and Patient Health Questionnaire Type 9 for Depression (PHQ-9) and the General Anxiety Disorder 7-item questionnaire (GAD-7). A reminder to complete these biweekly questionnaires will be sent to participant's cell phones via text message and on the tablets themselves. Additionally the application will send compliance messages to participants if participants do not fill out the fortnightly questionnaires.

- Between baseline visits (week 0 – 2) and between follow-up visits (week 10 -14) monitoring of pain at home – tablet only .

During these time periods participants will be asked to use the tablet with the application daily at night prior to sleep. Participants will be asked to complete a VAS of how they slept the night prior, a VAS of pain and asked to report the medications they used that day for pain management.

Description of Procedures Being Performed

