SECOND BASELINE CLINICAL ASSESSMENT (Week 2) - AT THE ARC OR VIA VIDEO CALL

Participant Information will be collected including:

- Record of changes in medications
- Record of changes in pain management techniques participants typically used
- Documentation of the location of their pain on a body chart

Participants will then complete the following questionnaires:

- Neuropathic Pain Symptom Inventory (NPSI)
- Pittsburgh Sleep Quality Index (PSQI)
- Beck Depression Inventory (BDI)

- Patient health Questionnaire Type 9 for Depression (PHQ-9)
- General Anxiety Disorder 7-item questionnaire (GAD-7)
- World Health Organization Quality of Life BREF (WHOQOL-BREF) & World Health Organization Quality of Life Pain (WHOQOL-pain)

Study Devices: Participants will be randomized into the Sham or Real study group arm and will undergo a Sana PR familiarization session:

ARM 1: Real

- Participants will be loaned a Sana PR device, headphones, charging cables and a strap to secure the device on their head
- The research team will download the Sana Health application on a tablet device compatible with the application that will be loaned to participants (this device will be a tablet that has all functions not necessary to the functionality of the Sana application disabled). The device will be loaned to participants for the duration of the 8-week intervention.
- The research team will teach the participant how to use the Sana PR device and the Sana Health application.

Participants will be given an instruction manual for the device and mobile application. Participants will be instructed to call the lab's direct phone-line [contact] if they have any additional questions when using the device at home.

- Participants will then complete their first 15 min session with the device in its normal settings under the supervision of the research team. For the Real arm, the session with the devices consists of periods of light/sound pulsing at three distinct pulse frequencies; ~8Hz, 3Hz, and 1Hz. For each frequency, there are distinct sections where the audio and visual pulses vary from eye to eye, and ear to ear. This first session will ensure the subjects know how to properly use the devices and that there are not any adverse events (AEs) from the first use of the device. Participants will be instructed to call the lab's direct phone-line [contact] if they experience an AE when using the device at home.

ARM 2: Sham

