We will use mixed modelling to determine the effect of the intervention on reported chronic pain – our primary outcome variable. We will also use ANOVAs (or their non-parametric equivalents) to assess changes in all of our outcome measures; including pain scores, sleep scores, device usage statistics, medication usage, heart rate variability, blood pressure, and quality of life measures.

6. Safety Assessment

Participants will be monitored for possible AEs throughout the study according to the frequency of the data review below. Participants will be given the email and phone number of the research team to report AE and circumstance of events. Participants will be reminded during the familiarization session with the device, at the second baseline visit, to seek immediate medical attention should they experience an injury as a result of being in the study. This will also be reiterated to participants if they reach out to report an AE. Data from the Sana Health application will be used to track compliance. Significant decrease in the compliance during (responding to less than 70% of the last 10 scheduled check-ins) of using the device the 8 week intervention will be considered an indication that a participant may need assistance. A research team member will call the participant to ensure that the reason of the drop in usage of the device is not due to an AE. Any AEs that occurs will be reported to the IRB to see if risk/benefit ratio is still acceptable for each individual participant and for the continuation of the study as a whole.

7. Benefits

Although no benefits can be guaranteed, it is possible that subject will experience a reduction in amount of chronic pain that they typically experience.

While there is no guarantee that this study will be beneficial to society, we hope that this study will help lead to the development of a device that can help reduce chronic pain and provide individuals who experience chronic pain with an alternative solution for managing pain.

8. Payment and Remuneration

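### Section 5 specifies no baseline covariate for its ANOVAs of change or its mixed model, although six questionnaire entries are scored twice before randomization; entering both scores as covariates needs no new data

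*Combined protocol and SAP*

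**What the plan says.** Section 5 (Data Analysis plan) has two sentences. The first covers the primary outcome: "We will use mixed modelling to determine the effect of the intervention on reported chronic pain". The second covers everything: "We will also use ANOVAs (or their non-parametric equivalents) to assess changes in all of our outcome measures". The outcomes it lists include pain and sleep scores and "device usage statistics, medication usage, heart rate variability, blood pressure, and quality of life measures". Neither sentence gives a covariate, a reference visit or a contrast between arms.

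Section 4 (Study Procedures) has two baseline visits, at week 0 ("INITIAL BASELINE CLINICAL ASSESSMENT (Week 0") and week 2 ("SECOND BASELINE CLINICAL ASSESSMENT (Week 2"). Each lists the same six questionnaire entries: NPSI, PSQI, BDI, PHQ-9, GAD-7, and one line holding WHOQOL-BREF and WHOQOL-pain. At week 2 the allocation step is listed after the questionnaires: "Participants will be randomized into the Sham or Real study group arm and will undergo a Sana PR familiarization session". The same six entries return at weeks 10 and 14.

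Daily pain on the VAS is rated once, before sleep, in weeks 0 to 2 and 10 to 14. In weeks 2 to 10 it is rated around each ad libitum device session and before the last use at night.

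**The concern.** The trial collects two pre-randomization scores on each questionnaire and does not say how either will be used. Change could mean change from week 0, from week 2 or from their mean, analysed as a simple change score or by repeated-measures ANOVA. These readings differ in precision. Choosing among them once data are in, across many outcomes, is a freedom that the plan should close beforehand. The mixed model for pain has the same gap.

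A change score fixes the baseline coefficient at 1. Unless that is the best coefficient, it discards information that regression on the baseline scores would keep. The stake is mainly precision at a fixed enrolment of 180.

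**Working it through.** **Inputs from the documents.** Enrolment goal 180 (Section 4, Subjects); two parallel arms; six entries at weeks 0, 2, 10 and 14. The 180 cannot be reproduced, because no alpha, power, effect size, SD or dropout is given.

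**Assumptions, not in the documents.** 1:1 allocation (90 per arm), no dropout, two-sided 5% tests, unit SD at each visit, and the correlations shown.

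**Why two separate covariates.** Every candidate analysis compares arms on Y − b0·(week 0) − b2·(week 2). Change from week 0 sets (b0, b2) = (1, 0); change from week 2 sets (0, 1); change from the mean sets (½, ½); adjusting for the mean forces b0 = b2. Regression on both scores picks the pair with the smallest residual variance. In large samples it therefore cannot do worse than any of these, whatever the correlations. This needs 1:1 allocation or the same covariances in both arms and, for the guarantee to hold at each visit, slopes that may differ by visit.

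**Equal correlation r among visits.** The two fitted coefficients are then equal, so separate covariates give the same precision as their mean.

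- Change from one baseline: 2(1 − r)
- Change from the two-score mean: 1.5(1 − r)
- Adjusted for both: 1 − 2r²/(1 + r)

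| r | one-baseline change | mean change | adjusted | SE cut vs one baseline | SE cut vs mean |
|---|---|---|---|---|---|
| 0.3 | 1.400 | 1.050 | 0.862 | 21.6% | 9.4% |
| 0.5 | 1.000 | 0.750 | 0.667 | 18.4% | 5.7% |
| 0.7 | 0.600 | 0.450 | 0.424 | 16.0% | 3.0% |
| 0.8 | 0.400 | 0.300 | 0.289 | 15.0% | 1.9% |

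The SE cut is 1 − √(adjusted ÷ comparator). At r = 0.5, SE = √(2 × variance ÷ 90) gives 0.1491, 0.1291 and 0.1217. Power for an assumed 0.35 SD difference at one visit is then 65%, 77% and 82%. To match 180 participants with adjustment, one-baseline change would need 180 × 1.000 ÷ 0.667 = 270, and mean change 180 × 0.750 ÷ 0.667, about 203. At r = 0.7 the powers are 86%, 94% and 95%.

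**Baselines closer to each other than to outcome.** With 0.8 between baselines and 0.5 with outcome, the variances are 1.000, 0.900 and 0.722. The SE cuts are 15.0% and 10.4%. Adjusting for a single baseline leaves 1 − 0.5² = 0.750, so most of this gain comes from adjusting at all.

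**Unequal correlations.** Take 0.8 between baselines, 0.8 for week 2 with outcome and 0.6 for week 0 with outcome.

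- Change from week 2: 2(1 − 0.8) = 0.400
- Adjusted for the mean: 1 − 0.7²/0.9 = 0.456, worse than change from week 2
- Adjusted for both separately: 1 − (0.64 + 0.36 − 2 × 0.8 × 0.6 × 0.8)/(1 − 0.64) = 1 − 0.232/0.36 = 0.356

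Separate covariates still win, but the SE cut against change from week 2 is 1 − √(0.356/0.400) = 5.7%, below the 15 to 22% range.

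**Cost.** Two covariates inflate the SE by about √(1 + 2/175) − 1 = 0.57% at 180, even if baseline were unrelated to outcome. At r = 0.8 the net cut against mean change is 1 − 0.981 × 1.0057, about 1.3%.

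**The case against.** Section 5 is silent; it does not exclude adjustment. A change score uses baseline by subtraction, and repeated-measures ANOVA remains open. This stands: a reader might infer that the plan rejects baseline adjustment or ignores baseline, and the text supports only that no baseline covariate is specified. Nor can a loss be claimed for the primary outcome, since the terms of its mixed model are not given.

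The gain may be small. This also stands. Against change from the two-score mean at r of 0.7 or 0.8 it is 2 to 3% of the SE, and the larger figures require change from a single baseline. A reader might also infer that adjusting for the mean of the two scores always beats change from one of them. The unequal-correlation case shows otherwise, which is the reason for separate covariates.

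A third objection concerns which contrast to test. A reader might take the order of the primary objective, which ends with "the long-lasting effect of pain relief at a 4-week follow-up using the following outcome measures", as a rule that week 10 is tested before week 14. The objective places both under the primary heading and states no hierarchy. Imposing one could cost power. At r = 0.5 with a 0.35 SD effect lasting to week 14, the adjusted week 10 contrast has 82% power. A pooled follow-up-versus-baseline contrast has 91% in a repeated-measures ANOVA and 95% with adjustment.

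**Conclusion.** The concern holds as a specification gap with a better method at almost no cost. No baseline covariate is specified, two pre-randomization scores exist for six questionnaire entries, and using both as covariates is in large samples at least as precise as any of the three change scores. The improvement is about 15 to 22% of the SE against one-baseline change and about 2 to 9% against mean change, under an assumed common correlation of 0.3 to 0.8 and 90 per arm. The direction does not depend on the correlations, apart from the small degrees-of-freedom cost; the size does.

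Three limits apply. The BDI gain is not quantified, because participants scoring above 30 at week 0 are withdrawn. The pre-randomization status of the week 2 scores rests on the order in which the visit is listed. And nothing here shows bias or an inflated false-positive rate from an ANOVA of change: a reader might infer that the planned analysis is invalid, but the documents support only that it is undefined and may waste information.

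**What to change.** For the six questionnaire entries, replace the ANOVA of change with a mixed model on the week 10 and week 14 scores. Include arm, visit and arm-by-visit, with the week 0 and week 2 scores as two separate covariates whose slopes may differ by visit. State a simple imputation rule, blind to arm, for a missing baseline score. Report the real-minus-sham difference at both visits, without a week 10 before week 14 testing hierarchy. State that the week 2 questionnaires are completed before allocation.

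Use the same baseline adjustment in the primary mixed model once the measure meant by reported chronic pain is named.

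For the daily pain VAS, compare the week 0 to 2 bedtime rating with the pre-sleep rating in weeks 2 to 10 and the bedtime rating in weeks 10 to 14, not with ratings around ad libitum sessions. Note that the questions may also differ: the intervention-period item asks about pain at that moment, while the other periods state no time frame.

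Do not extend the adjustment to outcomes with no pre-randomization value, such as device usage, heart rate variability and PGIC.

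The cost is SAP wording and two degrees of freedom per visit. No data, visits or participant burden are added.
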